Incisional negative pressure wound therapy for preoperatively irradiated pelvis and lower extremity soft tissue sarcoma wounds. A prospective, randomized pilot trial.

NCT02638298

Date Last Modified: April 21st, 2023

Principal investigator

[name]., MSCR

Associate [name]
Orthopaedic Oncology
Director of Orthopaedic Research
Associate Program Director
Medical University of South Carolina

[name]
[name]
[contact]
[contact]

Table of Contents

Hypothesis/Specific Aims.....	3
Background and Significance.....	3-5
Research Design.....	5-8
Methods.....	8-10
Budget.....	11-12
References.....	13

**Medical University of South Carolina
Protocol
PI Name: [name], MSCR**

Study Title: Incisional negative pressure wound therapy for preoperatively irradiated pelvis and lower extremity soft tissue sarcoma wounds. A prospective, randomized pilot trial.

A. HYPOTHESIS/SPECIFIC AIMS

The hypothesis of the proposed study is that use of a negative pressure wound therapy (NPWT) dressing on preoperatively radiated pelvic and lower extremity soft tissue sarcoma surgical wounds will significantly reduce the incidence and cost of wound complications.

This hypothesis will be tested through accomplishing the following specific aims:

- 1) Specific Aim 1- To estimate the wound complication rate of post-operative negative pressure dressings and traditional dry dressings, and risk of secondary interventions after resection of soft tissue sarcoma in lower extremities and the pelvis that have received pre-operative radiation. Wound complications are defined as a superficial infection, deep infection, need for prolonged (> 3 weeks) wound packing, or return to the operating room within six months for a secondary procedure. A secondary analysis of frequency and likelihood of antibiotic usage, pain scores, and functional scores will be analyzed in each group.
- 2) Specific Aim 2- To estimate the total cost of care and resource utilization in patients treated with negative pressure wound therapy and traditional dry dressings.

B. BACKGROUND AND SIGNIFICANCE

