No validated system is designed to specifically assess surgical wounds. The CDC definition is a stringent criterion to classify surgical site infection (SSI). Infections will be classified as superficial or deep and acute or delayed. Acute infection will be defined as within 6 weeks of the surgical procedure. Delayed or late infection will be defined as greater than 6 weeks from the surgical procedure.

Criteria for wound complication (SSI or surgical site infections)-

Table 1

SUPERFICIAL INFECTION (SSSI)	DEEP INFECTION (DSSI)
Involves skin and subcutaneous tissue (and)	Involves deep soft tissues (and)
a) purulent drainage	a) purulent drainage
b) organism cultured aseptically from wound	b) deep wound that spontaneously dehisces or is deliberately opened
c) deliberate opening of wound	c) an abscess or other evidence of deep infection
d) diagnosis of SSI by attending surgeon	d) diagnosis of SSI by attending surgeon

Superficial infection-

Infection occurs after any operative procedure,

and

involves only skin and subcutaneous tissue of the incision

and

patient has at least one of the following:

- a. purulent drainage from the superficial incision.
- b. organisms isolated from an aseptically-obtained culture of fluid or tissue from the superficial incision.
- c. superficial incision that is deliberately opened by a surgeon and is culture-positive or not cultured *and*
patient has at least one of the following signs or symptoms: pain or tenderness; localized swelling; redness; or heat. A culture negative finding does not meet this criterion.

d. diagnosis of a superficial incisional SSI by the surgeon or attending physician.

Deep infection-

Infection occurs after the operative procedure *and* involves deep soft tissues of the incision (e.g., fascial and muscle layers) *and* patient has at least one of the following:

- a. purulent drainage from the deep incision.
- b. a deep incision that spontaneously dehisces or is deliberately opened by a surgeon and is culture-positive or not cultured *and* patient has at least one of the following signs or symptoms: fever ($>38^{\circ}\text{C}$); localized pain or tenderness. A culture-negative finding does not meet this criterion.
- c. an abscess or other evidence of infection involving the deep incision that is found on direct examination, during invasive procedure, or by histopathologic examination or imaging test.
- d. diagnosis of a deep incisional SSI by a surgeon or attending physician.

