Analytic Approaches: To assess specific aim one patients will be followed longitudinally for the development of a wound complication and incidence of secondary procedures. Criteria for a wound complication are listed above. The data will be collected prospectively during routine follow up care of the patient and will include presence of absence of wound complication. The proportion of patients with a wound complication will be estimated and the 95% confidence for the true wound complication rate will be calculated with an exact binomial procedure. Although it is not the primary analysis, we will also compare the complication rates across the two groups using a Fisher's exact test (although the study is underpowered for this analysis). We will also use a logistic regression analysis where we adjust for center (using indicator variables) to estimate the overall wound complication rate in each group. For the risk of secondary interventions, the incidence of procedures performed for wound complications will be collected and multiple logistic regression analysis will be used to adjust these procedures in the incidence of wound complications.

To assess specific aim two the total cost of perioperative and post-operative care will be estimated from hospital billing records for patients. The median cost for the NPWT group and control group will be estimated and compared with independent t-test for normally distributed data and the Mann-Whitney test for any nonparametric data. A post hoc analysis of the cost of treatment for each arm will provide comparative effectiveness data for the use of NPWT in preoperatively radiated sarcoma surgical wounds. This is come directly from hospital and clinic charges, dressing and medication costs, and direct societal cost estimates from time missed from work.

Sample size justification: This is a pilot study with the primary objective of estimating complication rates in our patient population using NPWT and traditional dry dressings. We estimate that each of four institutions can enroll a least 40 patients over 36 months for a total of 160 patients. Assuming up to 5 patients in each group will have inevaluable data or follow-up, we plan on a total of 75 evaluable patients in each group. With 75 patients in each group and assuming complication rates of 10% to 30%, we have the following $\frac{1}{2}$ widths for 95% confidence intervals.

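### The only model stated for Aim 1's risk of secondary interventions has no sound reading, because it ties procedures to wound complications, which every counted procedure already implies

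*Combined protocol and SAP*

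**What the plan says.** Specific Aim 1 (section A) sets out to estimate the wound complication rate and the "risk of secondary interventions after resection of soft tissue sarcoma in lower extremities and the pelvis". The same aim lists, among the events that define a wound complication, "return to the operating room within six months for a secondary procedure".

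Under Statistical Considerations, Analytic Approaches, patients are followed for "development of a wound complication and incidence of secondary procedures", so the procedure is an outcome. Two statements then deal with it. One covers data collection: "the incidence of procedures performed for wound complications will be collected". The other, which is the only model given for procedures, reads: "multiple logistic regression analysis will be used to adjust these procedures in the incidence of wound complications".

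The exact binomial interval, Fisher's test and the "logistic regression analysis where we adjust for center (using indicator variables" are all written for the wound complication rate. No proportion by arm, interval or comparison is stated for procedures.

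Randomisation is before or at surgery (Research Design). Wounds are assessed from 2 weeks to 6 months after surgery (Postoperative Evaluations). The list of other data after Table 2 (section E, Methods) includes return to the operating room among items to be examined for association with wound complications.

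**The concern.** A wound complication arises after randomisation, and the protocol's hypothesis is that the dressing prevents it. A model that holds complications fixed while looking at procedures removes the route by which the dressing would reduce procedures. It answers a different question: among patients who had a complication, did the arms differ in how often a procedure followed?

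The nesting makes this acute. Only procedures done for wound complications are counted, so every counted procedure belongs to a patient with a complication. The plan says "Criteria for a wound complication are listed above" without showing whether it means the Aim 1 composite or the infection criteria under Wound Assessment. With either definition applied throughout, the nesting holds.

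At stake is one named Aim 1 quantity in a pilot whose product is its estimates.

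**Working it through.** **The plan's own figures.** Table 3 is the only stated precision, and it concerns complications. Exact (Clopper-Pearson) intervals with n = 75 and 8, 11, 15, 19 and 23 events give half-widths of 7.6, 8.6, 9.6, 10.4 and 10.9 points, as printed. One upper limit comes out at 19.9% against the printed 20.0%, which is immaterial. Table 3 is not in dispute.

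**Inputs.** From the documents: 75 evaluable patients per arm, and complication rates of 10% to 30% (Sample size justification). Assumed: complications p0 = 30% on gauze and p1 = 15% on NPWT, and f0, f1 = the share of complications that lead to a procedure, because the documents give no procedure rate.

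**Reading 1: procedures adjusted for, or restricted to, complications.** No patient without a complication can have a counted procedure, so the arm term is informed only by patients with one: 75 × 0.30 + 75 × 0.15 = 22.5 + 11.25, about 34 of 150. The arm odds ratio is

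[f1/(1 − f1)] / [f0/(1 − f0)],

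which does not contain p0 or p1. It equals 1 whenever f1 = f0.

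At f = 50% in both arms, expected procedures are 11.25 on gauze and 5.625 on NPWT. The odds ratio by randomised arm is (5.625 × 63.75)/(69.375 × 11.25) = 0.46. Among complications it is 1.00.

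| f gauze / NPWT | Procedure OR by arm (95% CI) | OR conditioned on complication (95% CI) |
|---|---|---|
| 50% / 50% | 0.46 (0.16, 1.34) | 1.00 (0.24, 4.18) |
| 50% / 20% | 0.18 (0.04, 0.76) | 0.25 (0.05, 1.34) |
| 50% / 70% | 0.66 (0.25, 1.76) | 2.33 (0.51, 10.66) |

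With equal f anywhere from 30% to 70%, and complications of 30%/15% or 20%/10%, the odds ratio by arm is 0.44 to 0.48 and the conditioned one is always 1.00.

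*Fitted check in whole numbers:* complications 22 v 12, procedures 11 v 6. Procedure on arm gives OR 0.506 (0.18, 1.45). Adding complication gives an arm OR of 1.00 (0.24, 4.08). The complication term separates and cannot be estimated (coefficient 24.6, SE about 12,000), while the arm term returns an ordinary-looking SE of 0.718.

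**Reading 2: complications adjusted for procedures.** Everyone with a procedure has a complication, so the arm term now comes from patients without a procedure. The unadjusted complication odds ratio is (0.15/0.85)/(0.30/0.70) = 0.41. After adjustment it is 0.41 × (1 − f1)/(1 − f0):

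- f 50%/50%: 0.41, unchanged
- f 50%/20%: 0.41 × 0.8/0.5 = 0.66
- f 50%/70%: 0.41 × 0.3/0.5 = 0.25

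Here the procedure term separates, and procedures have no arm analysis.

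**Event numbers for a replacement model.** At 20%/10% with f = 30%, expected procedures are 75 × 0.06 + 75 × 0.03 = 6.75 in total. The chance that at least one arm has none is 0.97^75 + 0.94^75 − (0.97^75 × 0.94^75) = 0.102 + 0.010 − 0.001, about 11%.

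**The case against.** The strongest reply is that the sentence is too garbled to convict. It could equally make complications the outcome and procedures the adjusting term, and the list after Table 2 partly supports that. The plan does not promise an arm comparison of procedures; that is inferred from Aim 1, which is about estimation. Counts by arm will be collected in any case.

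Much of this stands. A reader might infer that the plan definitely adjusts procedures for complications. The wording does not settle that, and the first table applies only if it does. The second reading is no refuge, though, since it is circular as well and leaves procedures without any analysis by arm. Collected counts are also not a stated analysis.

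A reader might further infer that an effective dressing would always show no effect on procedures. That is exact only when the same share of complications needs a procedure in both arms; at 50%/20% the conditioned odds ratio is 0.25.

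It can also be said that separation would alert the analyst. It would if complication is entered as a covariate, although the arm term still looks normal. If the analysis is restricted to patients with complications, nothing would show.

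**Conclusion.** The concern holds in this form: the only model stated for the risk of secondary interventions has no sound reading. This is more than missing detail, because following the sentence either way ties the analysis to a post-randomisation event nested with the outcome.

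Under reading 1 the procedure odds ratio can be made null (0.46 to 1.00), attenuated (0.18 to 0.25) or reversed (0.66 to 2.33). Under reading 2 the complication odds ratio stays at 0.41 or moves to 0.66 or 0.25. All these figures rest on assumed procedure shares and on complications of 30% v 15%. The intervals are wide, so the risk is a misplaced estimate rather than a false significant result.

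A reader might infer that the main Aim 1 results are compromised. They are not: the exact intervals, Fisher's test, the centre-adjusted complication model, Table 3 and the cost analysis do not depend on this sentence. It should be fixed, as a secondary matter.

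**What to change.** Replace the sentence on secondary interventions in Analytic Approaches with:

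> Procedure for a wound complication within 6 months (yes/no) is an outcome in all randomised evaluable patients. The proportion is reported by arm with an exact 95% CI. Any comparison between arms is adjusted for site only, using an exact or penalised (Firth) method if events are sparse or an arm or site has none. No variable arising after randomisation enters the model. The share of complications that needed a procedure is reported descriptively.

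The cost is one reworded sentence, with no new data, visits or patients. The exact interval and site adjustment are already planned for complications; the sparse-event method is the only addition. The downside is that the site-adjusted comparison will be imprecise with few events. With 6.75 expected procedures there would be about 1.7 per site at the four sites of the sample size text, or 1.1 at the six in Research Design.

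Reconciling the two wound-complication definitions is a separate matter and not part of this fix.

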For surgeons who must operate in an irradiated field there are several challenges. There is often a delay from the conclusion of radiation and the planned local control surgery (often between 3-6 weeks) to allow for the skin and soft tissue to recover. Despite this delay there is often evidence of soft tissue damage with skin erythema, tissue edema, and desquamation frequently observed. With large and deep tumors there is often tension on the wound edges at closure and a large amount of dead space from tissue and tumor removal. This often manifests postoperatively as a seroma which can further delay wound healing. Many of these patients will need vascularized tissue transfer for wound closure after sarcoma resection [4, 5]. This has added morbidity to the patient.

Patients who develop wound complications have been shown to longer hospitalizations and higher costs. The utilization of preoperative external beam radiation has been shown to increase the risk of postoperative wound complications [1, 6]. Anatomic location of the tumor has also been shown to be a risk factor for the development of wound complications with lower extremities being higher risk than upper extremities. There are several published studies examining the effect of negative pressure wound therapy on high risk surgical wounds. Abdominal wound complications have been shown to be reduced with the use of incisional NPWT[7]. In the orthopaedic literature the use of negative pressure incisional dressings have been shown to lower the risk of wound complications in total hip arthroplasty, ankle surgery, acetabular fractures, and extremity fractures[8-12]. Other wounds have been treated effectively with NPWT with good results include sternotomy wounds[13], cardiac surgery[14],

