The group of the Musculoskeletal Oncology Research Initiative (MORI) has successfully collaborated on several multi-institutional projects. This group of investigators had two poster presentation and a podium presentation at the 2013 Musculoskeletal Tumor Society Meeting in San Francisco. There are three projects in the submission phase for publication. This group consists of six executive members and twenty other musculoskeletal oncologists that are representatives of prominent academic institutions from across the country. The sites of the executive members will all participate. These sites are Stanford University, University of Iowa, Oklahoma University, Pacific Northwest University, and the Medical

University of South Carolina. Other sites may be asked to participate to ensure that the recruitment numbers are met within the enrollment period timeline.

To our knowledge, there have not been any published studies or preliminary data presented on the utility of negative pressure wound therapy in previously irradiated soft tissue sarcoma wounds. The benefits of improving wound healing in this cohort are self-evident. Reduction in major wound complications after oncologic resection of sarcomas in the setting of neoadjuvant radiation can provide improvement in quality of life, reduction in medical costs and office visits, and possibly improvement in pain and narcotic use. This high risk patient cohort could potentially benefit from reducing wound complications through NPWT and is an ideal population to study its effect. The impact of this novel and inexpensive intervention can have a profound impact on the care of sarcoma patients.

D. RESEARCH DESIGN

This study is designed as a prospective, multicenter randomized controlled pilot trial with competitive enrollment evaluating the risk of wound complications after surgical resection of extremity soft sarcomas that have undergone preoperative external beam radiation and then treated with Prevena™ or standard dry gauze dressing. Six sites are planned to participate with an average enrollment of 2-6 lower extremity sarcomas eligible for inclusion each month per site.

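### Aim 2 is to estimate cost, but the plan yields two medians and a p-value: no mean cost, cost difference or confidence interval is specified.

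*Combined protocol and SAP*

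**What the plan says.** Section A states Aim 2 as "To estimate the total cost of care and resource utilization in patients treated with negative pressure wound therapy" and, in parallel, in patients with dry dressings. The hypothesis in the same section is that NPWT "will significantly reduce the incidence and cost of wound complications".

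Under Statistical Considerations, Analytic Approaches, the source for Aim 2 is given: "the total cost of perioperative and post-operative care will be estimated from hospital billing records for patients". The method follows: "The median cost for the NPWT group and control group will be estimated and compared with independent t-test for normally distributed data". Where cost is not normally distributed, the plan names a second option: "the Mann-Whitney test for any nonparametric data". The same paragraph adds: "A post hoc analysis of the cost of treatment for each arm will provide comparative effectiveness data". It lists the components of that further analysis but no summary measure, contrast, interval or test.

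The only confidence intervals in the plan are exact binomial ones for the wound complication rate (Analytic Approaches and Table 3).

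**The concern.** The cost sentence does not hold together. It announces medians, but a t-test compares means and a Mann-Whitney test compares ranks. Which quantity is tested depends on how normal the data look.

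The normal branch is unlikely. Section B notes: "Patients who develop wound complications have been shown to longer hospitalizations and higher costs". The sample size paragraph assumes that 10% to 30% of patients have a complication. A costly minority on top of an ordinary base cost gives right skew, which leads to the Mann-Whitney branch. An aim worded as estimation would then end with two medians and a p-value.

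The choice of summary matters because total cost in an arm is the mean times the number of patients. The median does not deliver it. When most patients in both arms are uncomplicated, the median may respond little to savings made in the upper tail. A later trial or a comparative-effectiveness analysis needs the mean difference and its uncertainty.

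**Working it through.** **The plan's own figures.** No cost figure exists to reproduce. The sample size does reproduce: (4 × 40 − 2 × 5)/2 = 75 evaluable per arm. The Table 3 half-widths also reproduce with exact binomial limits at n = 75.

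**Precision without any dollar assumption.** With 75 per arm and a common SD, the 95% CI half-width for a mean difference is t(0.975, 148 df) × SD × √(2/75) = 1.976 × 0.1633 × SD = 0.323 SD. If SD/mean is 0.5, 1.0, 1.5 or 2.0 (assumed), this is about 16%, 32%, 48% or 65% of mean cost.

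**Illustration of mean against median (all cost inputs assumed).** Base cost is lognormal with median $30,000 and log-SD s. A complication adds a lognormal cost with median $40,000 and log-SD 0.5. The device costs $1,000. Complication rates (control v NPWT) are 30% v 15% or 20% v 10%, inside the plan's range.

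- Mean complication cost: 40,000 × exp(0.5²/2) = 45,326.
- Mean saving: 0.15 × 45,326 − 1,000 = 5,799, and 0.10 × 45,326 − 1,000 = 3,533.
- Median in an arm: the x that solves (1 − p) × P(base ≤ x) + p × P(base + complication ≤ x) = 0.5, with the device cost added for NPWT.
- Variance in an arm: V(p) = 30,000² × exp(s²) × (exp(s²) − 1) + p × 40,000² × exp(0.5) − (p × 45,326)².
- Half-width: 1.976 × √[(V(control) + V(NPWT))/75]. At 30% v 15% and s = 0.2 the SDs are 25,391 and 19,690, so the SE is 3,710 and the half-width 7,332. At s = 0.9 they are 55,957 and 53,611, giving 8,948 and 17,683.

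| Rates | s | Mean saving | Median difference | Ratio | Half-width |
|---|---|---|---|---|---|
| 30 v 15% | 0.2 | 5,799 | 1,217 | 0.21 | 7,332 |
| | 0.35 | 5,799 | 2,951 | 0.51 | 7,974 |
| | 0.5 | 5,799 | 4,461 | 0.77 | 9,163 |
| | 0.7 | 5,799 | 5,962 | 1.03 | 12,104 |
| | 0.9 | 5,799 | 6,989 | 1.21 | 17,683 |
| 20 v 10% | 0.2 | 3,533 | 122 | 0.03 | 6,312 |
| | 0.35 | 3,533 | 998 | 0.28 | 7,047 |
| | 0.5 | 3,533 | 1,840 | 0.52 | 8,369 |
| | 0.7 | 3,533 | 2,835 | 0.80 | 11,515 |
| | 0.9 | 3,533 | 3,665 | 1.04 | 17,285 |

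Simulated trials of 75 per arm give nearly the same average half-widths: about $6,200-9,300 at s = 0.2 to 0.5 and about $11,400-17,400 at 0.7 to 0.9. Coverage is close to 95%.

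**Wider grid.** Complication cost of $20,000, $40,000 or $80,000, five values of s and two rate pairs make 30 cells. The median difference is 0.02 to 1.33 times the mean saving: below it in 22 cells and above it in 8.

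**Power in the simulated trials.** At s = 0.2 to 0.5, Welch gives 12-33% and Mann-Whitney 5-21%. At s = 0.7 they give 16.0% v 16.0% (30 v 15%) and 8.7% v 7.8% (20 v 10%). At s = 0.9 they give 9.3% v 12.8% and 6.8% v 6.7%.

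**The case against.** The best defence is that this is a gap in specification, not in data. Billing totals are gathered per patient, so means can be computed later without loss. Software for the t-test usually prints a mean difference and its interval, and a further cost analysis by arm is mentioned. All of that is true. But the plan does not promise to report those outputs, the t-test applies only if cost looks normal, and the further analysis has no stated method. The gap in the written plan stands.

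It is also fair that the proposed interval is wider than the illustrated saving in every row of the table. A pilot can accept this: an honest wide interval is what an estimation aim should produce, and the plan already takes that approach for complication rates.

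Several stronger readings are tempting, and the documents do not support them.

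- A reader might infer that medians would hide a saving or reverse its sign. Direction and size depend on cost inputs that the documents do not give. With an assumed $3,000 device the median changes sign in 4 of the 6 cells with s up to 0.5, but that price is invented. Section B says only "this novel and inexpensive intervention". The contents page lists a budget section that is not in the text supplied, so absent prices cannot be held against the plan.
- A reader might infer that comparing means gains power. The advantage at s up to 0.5 disappears or reverses at 0.7 to 0.9.
- A reader might infer that time off work, a named cost component, is not collected. The list of record-based items under Postoperative Evaluations is introduced as examples, so omission from it and from Table 2 proves nothing.

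**Conclusion.** The point holds as a minor improvement to the second aim of a pilot. As written, the plan for Aim 2 specifies no mean cost, no between-arm cost difference and no interval for cost, and its one stated method pairs medians with tests that do not estimate a difference in medians. That conclusion rests on the text alone.

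The size of the consequence rests on assumptions. Skew is likely from the plan's own account of complication costs, but its extent is unknown. The illustration shows only that mean and median differences can diverge materially in either direction. The primary objective of estimating complication rates, the 75 per arm and Table 3 are not touched.

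**What to change.** In Analytic Approaches, replace the Aim 2 comparison sentence. The estimates should be (a) the arithmetic mean cost per patient in each arm through the 6-month visit, which is what the aim's wording asks for, and (b) the difference in means between arms, which the hypothesis asks for. Give each a 95% CI, using Welch or robust standard errors. Adjusting for center, as in Aim 1, is optional and is expected to add little. Keep medians as description and drop the choice of test based on normality.

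The cost is a few lines of wording, with no extra patients, visits or data. The drawback is a wide interval that is sensitive to a few very costly patients. The text should say so and should claim no gain in power.

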- Recurrent soft tissue sarcoma

Consent:

Subjects will be consented for participation in the study by one of the aforementioned investigating surgeons (or research team) at the time of their evaluation in the clinic or hospital setting. Consent will include permission to randomize dressing to either to negative pressure wound therapy or “standard” dry gauze post-surgical dressing. Standardized study consent forms will be signed by the investigating surgeon and the patient. Standard surgical consent for the assigned procedure will be done in accordance with the standard of care.

Randomization:

Randomization will be predefined at each site using block randomization to ensure that each site is balanced for each arm of the study. This block randomization will be distributed and managed centrally at The Medical University of South Carolina. The randomization process will be performed centrally at MUSC and the treating surgeon will not have access to that randomization list. Preoperatively, the subjects will be blinded as to which dressing will be used for surgical wound coverage, but which dressing (i.e. which treatment arm) the patient was randomized to receive will be apparent postoperatively. Due to the design of the study, the surgeons are not able to be blinded.

Preoperative Evaluation:

Patients will receive the standard workup of a soft tissue sarcoma. The patient’s preoperative evaluation or treatment plan will not be affected by this investigation or the subjects desire to participate. Data collected preoperatively will include radiation type and dose, use of chemotherapy, VAS pain score, MSTS score, PROMIS Global Health score, medical comorbidities, tumor location, and any use of pain medicines.

Operative Intervention:

Surgery will be done in accordance with the standard of care for the excision of soft tissue sarcomas.

Anesthesia: Either regional or general anesthesia will be performed at the discretion of the treating physicians. Skin will be closed with either staples or 2-0 nylon sutures and a temporary closed suction drain may be placed. The use and duration of the drain will be at the surgeon’s discretion and in accordance with practice.

Tumor excision/limb reconstruction:

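### The Aim 2 cost comparison leaves out site although randomization is blocked by site: the test is unbiased but conservative, and it gives up some power

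*Combined protocol and SAP*

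**What the plan says.** The design section describes a "prospective, multicenter randomized controlled pilot trial with competitive enrollment". It states that "Six sites are planned to participate", while the sample size justification counts on four institutions with 40 patients each. Under Randomization (section D), allocation is made "using block randomization to ensure that each site is balanced for each arm of the study".

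For Aim 2 (section E, Statistical Considerations, Analytic Approaches), the "total cost of perioperative and post-operative care will be estimated from hospital billing records for patients". A further cost analysis in the same paragraph draws on "hospital and clinic charges, dressing and medication costs, and direct societal cost estimates from time missed from work". A median is estimated per arm, and the arms are "compared with independent t-test for normally distributed data", with a Mann-Whitney test otherwise. No site term, stratification or within-site summary for cost appears anywhere in the document. No interval for cost is planned.

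The preceding paragraph, on Aim 1, includes a logistic model for wound complications that adjusts for center with indicator variables.

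**The concern.** Each hospital's price level enters the outcome directly, because the data are that hospital's own charges. Blocking by site puts about the same number of patients from each hospital in each arm, so price levels cancel from the difference between arms. A pooled two-sample test does not use this. It treats the spread between hospitals as patient-level noise and judges the difference against a variance that is too large.

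A real cost difference is then more easily missed, because of variation that says nothing about the dressing. Cost is one of the two specific aims and part of the stated hypothesis, and the sample size was not set with cost in mind, so no planned margin absorbs the loss. A pooled SD carried from this pilot into a later site-stratified trial would also overstate the variance.

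**Working it through.** **Figures in the plan.** The sample size justification gives 4 × 40 = 160 patients, less up to 5 per arm: 160 − 10 = 150, or 75 per arm. Table 3 covers complication rates only and reproduces with exact binomial limits (15/75 gives 11.6% to 30.8%, half-width 9.6). There is no SD, target difference, power or between-site spread for cost, so the plan has no cost figure to reproduce.

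**Assumptions (not in the documents).** Lognormal cost; within-site SD of log cost σ = 0.7; four sites of near-equal size; 75 per arm, balanced within site; two-sided 5%; effect = 30% lower cost. The SD of site levels on the log scale, s, is 0, 0.2, 0.3, 0.4 or 0.5.

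**Formulas, log cost.**
- Share of variance explained by site = s² / (s² + σ²).
- With arms balanced within site, the true variance of the arm difference is 2σ²/75. The pooled test uses about 2(σ² + s²)/75. The standard error ratio is therefore r = √(1 + s²/σ²) = 1/√(1 − share).
- True size = 2[1 − Φ(1.96 r)].
- Power = Φ(z − 1.96 r), where z = |ln 0.7| / (0.7 √(2/75)) = 0.357/0.1143 = 3.12. With site in the model r = 1 and power = Φ(1.16) = 87.7%.

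**Example, s = 0.3.** Share = 0.09/0.58 = 16%. r = √(1 + 0.09/0.49) = 1.088. Size = 3.3%. Power = Φ(3.12 − 2.13) = 83.8%, a loss of 3.9 points.

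| Site share | SE excess, log cost | Size, log cost | Power, pooled v adjusted, log cost |
|---|---|---|---|
| 0% | 0% | 5.0% | 87.7 v 87.7 |
| 8% | 4% | 4.2% | 86.0 v 87.7 |
| 16% | 9% | 3.3% | 83.8 v 87.7 |
| 25% | 15% | 2.4% | 80.6 v 87.7 |
| 34% | 23% | 1.6% | 76.2 v 87.7 |

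**Dollars and ranks, by simulation.** Same set-up, 3,000 trials per cell; Monte Carlo error is about 0.4 points for size and 0.7 to 0.9 for power.

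| Site share | SE excess, dollars | Size: t in dollars / Mann-Whitney | Power in dollars: t v site-adjusted | Power: Mann-Whitney v van Elteren |
|---|---|---|---|---|
| 0% | 0% | 5.0% / 5.1% | 77 v 77 | 85 v 84 |
| 8% | 3% | 4.3% / 3.7% | 75 v 77 | 84 v 85 |
| 16% | 6% | 3.7% / 3.8% | 72 v 77 | 81 v 85 |
| 25% | 10% | 3.3% / 2.5% | 67 v 74 | 78 v 85 |
| 34% | 15% | 2.4% / 1.6% | 62 v 72 | 73 v 85 |

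Repeat simulations agree closely at the smaller shares. At 34% they spread more and reach 14 points in some, so I quote 11 to 14 there.

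**Another parametrization.** If sites are random draws with intraclass correlation ρ, then r = √(1 + [ρ/(1 − ρ)] (S − 1)/S) for S sites. Set the effect so that the adjusted test has 80% power. With four sites, ρ = 0.05, 0.10, 0.20 and 0.30 give standard errors 2.0%, 4.1%, 9.0% and 15.0% too large, and power of 78.9%, 77.7%, 74.7% and 70.8%. With six sites, ρ = 0.30 gives 16.5% and 69.8%. These excesses are smaller at a similar-looking percentage because ρ is a population quantity, whereas the share above is what the actual sites explain.

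**The case against.** The strongest reply is that the size is wholly assumed. The documents give no cost variance and no between-hospital spread. If site explains 8% of the variance or less, the loss is one or two power points. That stands, and it is why the range starts at zero.

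Second, the largest standard error figures belong to log cost, and the plan mentions no log transformation. In dollars the excess is about two-thirds as large. That stands too. The t-test is also reserved for normal data, so skewed costs would go to Mann-Whitney. The rank-test losses are much the same, so this does not remove the point.

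Third, the contrast with Aim 1 is only partial. The exact binomial estimates and the Fisher's exact comparison of complications are also unadjusted; center enters only through the additional logistic model. So one cannot say that the plan adjusts every comparison except cost. It does show that a center-adjusted model is already within the plan.

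Fourth, Aim 2 is a secondary, estimation-oriented aim of a pilot whose sample size rests on complication rates. That limits the weight of the point.

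Three stronger readings are tempting and not supported. A reader might infer that hospital price differences bias the cost contrast or create false positives. Blocking within site prevents the first, and the pooled test errs on the conservative side. A reader might infer that published cost intervals will be too wide, but the plan specifies no interval for cost; the point concerns the test, and any interval later built on the same pooled standard error. A reader might infer that a large loss has been shown. It has not, because the between-site spread is unknown.

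**Conclusion.** The point holds as a matter of efficiency. The plan randomizes within site and then tests cost as if site did not exist, so the test is conservative and some power is lost. Under the stated assumptions, as the site share rises through 8%, 16%, 25% and 34%, true size falls from 5% to about 4%, 3–4%, 2.5–3% and 1.5–2.5% (the upper end of the last range is for dollars). The power loss is about 1–2, 4, 7 and 11–14 points, and Mann-Whitney against van Elteren shows nearly the same. With no site difference nothing is lost. The direction follows from the design; the size depends on a between-hospital cost spread that the documents do not give. The validity of the cost comparison is not in question.

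**What to change.** In the Aim 2 paragraph of Analytic Approaches, state that cost will be analysed within site. Estimate the cost difference from a model with arm and site indicators, name the scale of analysis, and report an interval obtained by resampling patients within site and arm. If a rank test is kept, replace Mann-Whitney with the site-stratified van Elteren test. Show cost by arm within each site as a descriptive table.

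The cost is a sentence or two in the plan, a little programming, and three degrees of freedom with four sites or five with six, out of about 150. No new data are needed, and nothing in treatment or follow-up changes.
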